5.8 Laboratory Assessments

Laboratory assessments of genetic polymorphisms and urinary leukotriene are specified in section 10 of this protocol will be performed according to approved standard operating procedures (SOPs).

5.9 Radiology or other Procedure

No radiological examination will be performed for study purposes. Other procedures to be performed are:

Weight: Weight in light clothing will be measured with weighing scales and

recorded in kilograms

Height Height without shoes will be measured using a stadiometer.

Salivary sample: Saliva for DNA will be collected using the Oragene-infant sponge system.

The sponge tips are cut into an Oragene DNA kit to preserve the DNA and prevent bacterial growth. This method yields high-quality DNA and

eliminates the need for traditional cheek scraping methods.

ALOX5 polymorphism status will be determined within 1 week of sampling in the ICMS laboratory. DNA is extracted according to a SOP and the manufacturer's instructions (DNAgenotek). Products of the PCR are analysed by capillary electrophoresis on a 3130xl Genetic Analyser (Applied Biosystems). Fragments are obtained, varying in size depending on the copy number of the repeat sequence, and are visualized using GeneMapper v4 software. Genotypes will be called from duplicate amplifications with respect to standards run on each plate that are verified by direct DNA sequence analysis. Within 24 months of collection we will assess 150 polymorphisms in 10 genes encoding components of

the LT biosynthetic pathway and the LT receptors ALOX5, ALOX5AP, LTC4S, CYSLTR1, CYSLTR2, PLA2G4A, LTA4H, LTB4R1, LTB4R2 and MRP. These included all SNPs located in promoter regions, exons and intron-exon boundaries and the SNPs within the ALOX5AP haplotypes (referred to as Hap A and Hap B). Additional tagSNPs will be selected using the LDselect algorithm on the basis of linkage disequilibrium patterns across the genes using data from both our own previous studies in cardiovascular disease and asthma as well as resequencing data available from the Seattle SNPs and NIEHS SNPs databases. SNP genotyping will be carried out using the KASPar competitive allelespecific PCR method (Kbiosciences, Hitchin, UK).

Urine sample

A urine sample will be obtained from children in spontaneously voided urine using an age-appropriate method into a sterile receptacle. A first urine sample will be obtained when patients are well and a second during an acute wheezing illness if possible. Urinary leukotriene level will be assessed using a HPLC-mass spectrometry technique. Values will be indexed to urinary creatinine.

5.10 Unblinding procedures

At the time of generating the randomisation code described in 5.3, Nova Laboratories Ltd will also prepare 2 opaque envelopes, each containing a copy of the randomisation code detailing the active/placebo allocation associated with each randomisation number. The trial pharmacist will hold a copy of the randomisation code.

These envelopes may only be opened in the following circumstances:

1. Emergency code break:

A Principal Investigator, or physician covering for that Principal Investigator in his / her absence, may request an emergency code break in the following circumstances:

- a) in case of a suspected severe adverse reaction (SAR) where knowledge of patient allocation may influence clinical management of a study participant
- b) in case of a suspected unexpected severe adverse reaction (SUSAR)
- c) in any other circumstance in which the PI considers that an emergency code-break is indicated

2. Non-emergency code break:

a) A Trial pharmacist will be unblinded in order to reissue medications should a subject misplace or exhaust their supply of IMP, or if their IMP supply reaches its expiry date. Other trial staff will remain blinded.

b) A general code-break will occur at the end of the trial, to allow data analysis.

5.11 Withdrawal

5.11.1 Withdrawal of Subjects

Children will be withdrawn from the study if their parents withdraw consent to participate, if their allocation is unblinded, or if an investigator concludes that this course of action is in the child's best interests. Children will also be considered to have withdrawn if their parents consistently fail to respond to telephone calls at scheduled telephonic review. They will also be withdrawn if they are commenced on regular montelukast by their usual practitioner.

5.11.2 When and How to Withdraw Subjects

Children may withdraw from the trial, or be withdrawn from the trial, in the circumstances described in section 5.11.1. If a child withdraws or is withdrawn, from the trial, the reason for withdrawal will be recorded in the case report form. When a parent fails to respond to telephone calls at scheduled telephonic review, research nurses or research assistants will make appropriate attempts to contact the parent.

5.11.3 Data Collection and Follow-up for Withdrawn Subjects

Parents of all children who withdraw prematurely from the study will be asked if they agree to continuing telephone calls as detailed in the schedule above. Data collected will be included in study analyses.

6 Investigational medicinal products

6.1 Definition of each IMP

6.1.2 Active drug

Trade name: Singulair Granules

Composition: 4mg Montelukast sodium (which is equivalent to 4mg montelukast)

granules with mannitol exipient

ATC code: R03DC03
Pharmaceutical form: Granules

Dosage regimen: One sachet to be given once a day at the start of a cold or wheezy

episode, and continued for 10 days.

Route of administration: Oral

Manufacturer Merck Sharpe and Dohme Ltd (purchased on the open market)

6.1.3 Placebo

Trade name: Mannitol EP (Pearlitol SD 200)

Composition: Mannitol Granules

ATC code: Not applicable; drug master file lodged with the European

Pharmacopoeia commission

WAIT Trial_ Protocol_v7_24th June 2011

Page 30 of 58

Protocol as approved by National Research Ethics Service Reference 09/H1102/110 Date 23rd November 2009 Pharmaceutical form: Granules

Dosage regimen: One sachet to be given once a day at the start of a cold or wheezy

episode, and continued for 10 days.

Route of administration: Oral

Manufacturer Roquette Pharma

6.2 Product sourcing, manufacture and supply

Authorisation number: MIA(IMP) 13581

Authorisation holder: Nova Laboratories Ltd., [name],

[name]

6.3 Pre-medications

Not applicable.

6.4 Prescription of IMP

Trial delegation logs will specify the names of physicians authorised to prescribe IMP for this study.

6.5 Preparation and Administration of IMP

IMP will be prepared by Nova Laboratories Ltd, and shipped to pharmacy at The Royal London Hospital and additional sites. Administration of IMP is to be commenced by the parent or guardian at home at the onset of every viral upper respiratory tract infection or wheeze episode and continued for 10 days. Parents will be advised to store the IMP at room temperature, out of the reach of children, and instructed on when to initiate and stop treatment

6.6 Prior and Concomitant Therapies

Prohibited concomitant therapies are:

Montelukast granules
Treatment with another IMP

6.7 Dose modification/reduction/ delay

Administration of IMP will be discontinued in the following circumstances:

1. If the child is prematurely withdrawn from the study because their parents withdraw consent to participate.

WAIT Trial_ Protocol_v7_24th June 2011

Page 31 of 58

- 2. If an investigator concludes that this course of action is in the child's best interests.
- 3. If a child is prescribed regular daily montelukast by a clinician.

6.8 Toxicity profiles

The toxicity profile of montelukast granules is minimal and is described in the SPC¹². This will be reviewed annually and updated if relevant new data come to light.

6.9 Labelling and Packaging

IMP will be labelled and packaged by Nova Laboratories Ltd. according to principles of GMP. IMP will be packaged into white sachets.

6.10 Blinding of IMP

All the following individuals will be blinded to the IMP allocation, the parent, the child, the research nurse, the local and chief PIs. Active and placebo batches of IMP will have identical packaging, labelling and appearance.

6.11 Receipt of IMP Supplies and Storage of IMP

Participating pharmacies will inform the Chief Investigator on receipt of IMP deliveries. IMP will be stored in the pharmacy according to GCP principles.

6.12 Dispensing of IMP

Research nurses or research assistants will withdraw IMP from the participating site pharmacy on behalf of study participants on production of a signed trial prescription. Parents will be supplied with their first supply of IMP sachets at visit 2 (T0) and issued with a replacement box when that supply expires or is exhausted/misplaced.

6.13 Return and Destruction of IMP

Research nurses or research assistants will return unused or expired IMP to the participating site pharmacy where it will be destroyed according to local standard operating procedures.

7 Pharmacovigilance

7.1 General definitions

7.1.1 Adverse Events (AE)

An AE is any untoward medical occurrence in a subject (in this case "child") to whom a medicinal product has been administered, including occurrences which are not necessarily caused by or related to that product. An AE can therefore be any unfavourable and

unintended sign (including an abnormal laboratory finding), symptom or disease temporally associated with the use of an IMP, whether or not it is considered related to the IMP. Viral respiratory tract infections and wheezing episodes that trigger IMP initiation will not qualify as AEs as their temporal relationship to IMP use is predetermined by the protocol.

7.1.2 Adverse Reaction (AR)

An AR is any untoward and unintended response in a child to an IMP, which is related to any dose administered to that subject. All adverse events judged by either the reporting investigator or the Sponsor as having a reasonable causal relationship to a medicinal product qualify as adverse reactions. The expression reasonable causal relationship means to convey in general that there is evidence or argument to suggest a causal relationship.

7.1.3 Serious Adverse event (SAE) or Serious Adverse Reaction (SAR)

Serious Adverse Event (SAE)

A SAE is an AE that fulfils at least one of the following criteria:

Is fatal – results in death (NOTE: death is an outcome, not an event)

Is life-threatening

Requires inpatient hospitalisation or prolongation of existing hospitalisation

Results in persistent or significant disability/incapacity

7.1.4 Suspected Serious Adverse Reaction (SSAR)

An SSAR is an adverse reaction that is classed as serious and which is consistent with the information about the medicinal product as set out in the Summary of Product Characteristics (SmPC) or Investigator's Brochure (IB) for that product.

7.1.5 Suspected unexpected Serious Adverse Reaction (SUSAR)

The definition of a SUSAR is any suspected unexpected adverse reaction related to an IMP that is both unexpected and serious. In this case the event is not outlined in the Summary of Product Characteristics (SmPC) or Investigator's Brochure (IB) for that product.

7.2 Investigators' Assessment

7.2.1 Seriousness

Responsibility for evaluation of seriousness of adverse events will be shared between the treating principal investigator and the chief investigator, according to criteria specified above.

7.2.2 Causality

Responsibility for evaluation of causality of adverse events will be shared between the treating the chief investigator and clinical co-principal investigators.

[figure not shown]
7.2.3 Expectedness

Responsibility for evaluation of expectedness of adverse events will be shared between the treating clinical co-principal investigators and chief investigator.

7.3 Notification and Reporting of Adverse Events or Reactions

Adverse events or reactions will be notified and reported according to the flowchart below.

7.3.1 Flowchart summarising procedures for notification and reporting of adverse events

Protocol as approved by National Research Ethics Service Reference 09/H1102/110 Date 23rd November 2009

WAIT Trial_ Protoc

7.4 Notification and Reporting of Serious Adverse Events / SUSAR

7.4.1 Recording SARs

As the IMPs used in this project are licensed in the UK, the expected SARs (outlined in the SmPC) will be recorded in the CRF. SAE forms for these SARs will not be sent to the sponsor. In addition, the population of children entered on this trial (children with at least 2 episodes of wheeze aged 10 months to 5 years inclusive at recruitment) will be expected to be hospitalised as part of their clinical care for the following reasons:

- 1. Exacerbation of wheeze
- 2. Acute lower respiratory tract infection
- 3. Acute febrile illness
- 4. Febrile convulsion
- 5. Gastroenteritis
- 6. Exacerbation of eczema

The SAEs above will be recorded in the CRF, but they will not be recorded on SAE forms or reported to the sponsor as they are classified as expected.

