9.6.2 Monitoring procedures

The DMC will review accumulating data in a blinded fashion in order to monitor safety, efficacy and quality of study conduct. The DMC may also request data presented in an unblinded form.

a) Safety monitoring

The DMC may ask for an analysis to compare the incidence of fatal/life-threatening events and other SAE between the 2 groups, and report any need for changes in the conduct of the trial to the Steering Committee.

b) Efficacy monitoring

No interim efficacy analysis will is planned.

WAIT Trial_ Protocol_v7_24th June 2011

Page 39 of 58

c) Monitoring quality of study conduct

If the DMC observes problems with the study conduct (e.g. with respect to protocol adherence or withdrawal of children), it should consider making recommendations to the investigators and the sponsor to improve the quality of the study.

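### Section 7.4.1 exempts six causes of hospitalisation from SAE reporting with no condition on relatedness to the IMP, which conflicts with the protocol's own SUSAR rules

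*Protocol*

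**What the plan says.** Protocol section 7.4.1 creates two exemptions from SAE forms.

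- **Product-based.** Because the IMPs are licensed, "the expected SARs (outlined in the SmPC) will be recorded in the CRF", and no SAE form for these goes to the sponsor.
- **Population-based.** The section then adds that children in this trial "will be expected to be hospitalised as part of their clinical care for the following reasons". It lists worsening wheeze, lower respiratory infection, febrile illness, febrile convulsion, gastroenteritis and worsening eczema. These SAEs go in the CRF, but "they will not be recorded on SAE forms or reported to the sponsor as they are classified as expected".

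Section 7.1.5 defines a SUSAR as "any suspected unexpected adverse reaction related to an IMP that is both unexpected and serious", and treats an event as unexpected when it is not outlined "in the Summary of Product Characteristics (SmPC) or Investigator's Brochure (IB) for that product".

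Section 7.4.2 sends SUSARs to the JRO and the main REC within one working day. Section 7.5 has the allocation of a child with a suspected SUSAR unblinded and the case reported to the sponsor, which informs the MHRA if the child was on montelukast. Sections 7.2.2 and 7.2.3 give the investigators responsibility for judging causality and expectedness of adverse events.

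**The concern.** The protocol uses the word expected in two senses. In 7.1.5 it means that the product information already describes the reaction. In 7.4.1, for the six listed causes, it means that children like these are often admitted for such reasons anyway. The second sense says nothing about whether a particular admission was caused by the drug, yet it is used to switch off reporting.

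A site that follows 7.4.1 as written could leave a suspected, serious reaction that is absent from the SmPC in the CRF, with no SAE form and no notice to the sponsor. Section 7.1.2 makes an event an adverse reaction if either the investigator or the sponsor judges it causally related, and a sponsor that receives no report is poorly placed to make that judgement. Relatedness is also not an idle question here. Section 1.5.1 reports a slight excess of ear infection, sore throat and upper respiratory infection on montelukast in paediatric studies. That does not show that any listed cause is drug-related, but it does show why causality should be judged case by case.

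**Working it through.** No figure in the protocol bears on this point, so the check is a comparison of rules. The table takes an admission for one of the six listed causes and applies each rule to it.

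| Listed admission | 7.1.5, 7.4.2 and 7.5 | Six-cause sentence in 7.4.1 | Result |
|---|---|---|---|
| Judged unrelated to IMP | Not a SUSAR | CRF only | No conflict |
| Judged related, outlined in SmPC/IB | Expected reaction, not a SUSAR | CRF only, as for SmPC-outlined SARs | No conflict |
| Judged related, not outlined in SmPC/IB | SUSAR: report within one working day, unblind, inform sponsor | CRF only, no SAE form, no sponsor report | Rules cannot both be followed |
| Judged unrelated, fatal or life-threatening | Not a SUSAR | CRF only, if read literally | Gap, no contradiction |

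Four points support the third and fourth rows.

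1. The six causes do not rest on the SmPC. Section 7.4.1 deals with SmPC-outlined reactions first and introduces the six causes as an addition, justified by the population.
2. The six-cause sentence does not mention relatedness. The causality and expectedness assessments in 7.2.2 and 7.2.3 exist, but 7.4.1 does not make its exemption depend on them.
3. No visible text says which rule prevails. Section 7.6 only repeats that expected and non-reportable events are recorded in the CRF.
4. On outcome, 7.1.3 notes that "death is an outcome, not an event". A death from a listed cause would therefore stay under its listed heading, and 7.4.1 has no exception for it. Outcome plays no part in the expectedness test of 7.1.5, so this is an omission in 7.4.1 and not a clash between sections.

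**The case against.** The strongest reply is that the sections can be read together. The six-cause sentence speaks of SAEs, while SARs are handled separately just before it. Sections 7.4.2 and 7.5 are unconditional about SUSARs, and causality is assessed for adverse events generally. On that reading, background admissions are exempt and suspected reactions meeting 7.1.5 are reported. The reading is sensible and may be what was intended, but 7.4.1 does not state that precedence. Its heading concerns SARs, and the reason it gives for non-reporting is the label expected, the very term on which the SUSAR definition turns.

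Section 7.3 also refers to a flowchart in 7.3.1 that is not visible in the text available. It may contain a causality or fatality step. If so, the wording of 7.4.1 would still have to be aligned with it.

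Exempting common childhood admissions from expedited reporting while keeping them in the CRF is a reasonable design choice, and this point does not dispute it.

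A reader might infer three stronger things that the protocol does not support.

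- **That emergency unblinding would be blocked.** Section 5.10 lets a Principal Investigator request a code break for a suspected SAR, a suspected SUSAR or any other circumstance thought to need it. Section 9.6.1 has pharmacy act on such a request. Neither depends on an SAE form.
- **That the DMC would not see these admissions.** Section 9.6.2 says "The DMC may ask for an analysis to compare the incidence of fatal/life-threatening events and other SAE between the 2 groups", and nothing says that such an analysis is built from SAE forms. The events are in the CRF, 9.1.6 puts CRF data in the trial database, and admissions and mortality are listed outcomes in 10.1.2.
- **That the sponsor is wholly blind to them.** Section 9.5 gives it direct access to source data, and 7.4.3 provides annual safety reports. These routes are slower than one working day, but they exist.

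**Conclusion.** The concern holds in a limited form. For a listed admission judged related to the IMP and not outlined in the SmPC or IB, 7.4.1 conflicts with 7.1.5, 7.4.2 and 7.5, and following 7.4.1 literally would suppress a reportable reaction. The missing exception for fatal or life-threatening cases is a separate gap.

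No count can be attached. The protocol gives neither an admission rate for the six causes nor the share likely to be judged related. A count of all listed admissions would measure the wrong thing, since most would presumably be unrelated and properly exempt. Under 7.1.1, moreover, the infections and wheezing episodes that trigger IMP use do not qualify as adverse events at all.

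It would go too far to say that the protocol deliberately exempts these admissions whatever their cause or outcome. It does not say so; the breadth comes only from the absence of a qualifier. The conclusion assumes that at least one of the six causes is not outlined in the SmPC, which cannot be checked from the protocol, and that the 7.3.1 flowchart does not override the text.

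**What to change.** Reconcile 7.1.5, 7.4.1, 7.4.2 and 7.5. Add a sentence to 7.4.1 limiting the six-cause exemption to listed hospitalisations that the investigator judges unrelated to the IMP and that are neither fatal nor life-threatening. All other listed events should follow 7.4.2 and 7.5, with the SmPC/IB test of 7.1.5 deciding whether a related event is a SUSAR. Check the 7.3.1 flowchart against the revised wording.

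The cost is a sentence of text and a few extra SAE forms. The CRF already records these events, and the large majority of routine admissions should remain exempt. The change concerns reporting only and does not alter treatment or clinical care.

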7.4.2 Unexpected SAEs

Unexpected SAEs will be recorded in the CRF and on the sponsor SAE form and reported to the JRO within one working day of the PI or co-investigators becoming aware of the event. The co-investigators listed in this protocol/appendix will be authorised to sign the SAE forms in the absence of the PI. SUSARs arising during the trial will be reported to the JRO and the main REC within one working day of the PI or co-investigator becoming aware of the event.

7.4.3 Annual Safety Reports (ASR)

Annual Safety Reports (ASR) will be sent by the CI to the sponsor, the MREC and the MHRA on the anniversary of the date on the "notice of acceptance letter" from the MHRA using the sponsor ASR form. The ASR will state whether new findings for the subjects of the trial have changed the benefit / risk ratio of conducting the trial.

7.4.4 Annual Progress Reports

Annual Progress Reports will be sent to the main REC and to the sponsor on the anniversary date on the MREC "favourable opinion" letter.

7.5 Procedures for reporting Blinded SUSAR

The allocation of any study participant experiencing a suspected SUSAR will be unblinded according to the WAIT Trial Standard Operating Procedure for emergency code breaking, and reported to the Sponsor. If allocation is to montelukast granules, the sponsor will report the SUSAR to the MHRA.

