9.6 Data Monitoring Committee

A data monitoring committee (DMC) has been established for the trial. The chairman of the DMC will keep a record of DMC communications and activities. The central responsibility of this DMC will be to make recommendations to the Sponsor and the Chief Investigator on further conduct of this trial, based on results of the monitoring procedures described below. Such recommendations could include continuing or terminating the trial, or modifying its protocol. Any such modifications should not violate the concepts behind the original study protocol. If changes in the study conduct are recommended by this DMC, sufficient information should be provided to allow the sponsor and chief investigator to decide whether and how to implement them. The implementation of any DMC recommendation is the responsibility of the sponsor and chief investigator who are also free to neglect (in whole or in part) any recommendations of this DMC. The sponsor and the investigators bear the final responsibility for the conduct of the trial. This responsibility cannot be transferred to the DMC.

9.6.1 Maintenance of trial treatment randomisation codes and procedures for breaking codes.

The trial treatment randomisation code will be generated by Nova Laboratories Ltd as described above. Nova Laboratories Ltd will email a copy of this code to the Trials pharmacist at the participating sites hospital pharmacy. A member of the participating sites hospital pharmacy staff may unblind a participant's allocation at the request of a Principal Investigator, according to the WAIT Trial Standard Operating Procedure for emergency code breaking.

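### Unblinding a suspected SUSAR for regulatory reporting runs through the PI-requested emergency code break, which probably discloses the arm to a blinded investigator and, as 5.11.1 is worded, withdraws the child

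*Protocol*

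**What the plan says.** Protocol section 7.5 makes unblinding compulsory: "The allocation of any study participant experiencing a suspected SUSAR will be unblinded". The route it names is the SOP for emergency code breaks. The result goes to the sponsor, and one use is given for it: "If allocation is to montelukast granules, the sponsor will report the SUSAR to the MHRA".

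Section 9.6.1 describes who operates that SOP. Personnel of the site's pharmacy "may unblind a participant's allocation at the request of a Principal Investigator, according to the WAIT Trial Standard Operating Procedure for emergency code breaking". Section 5.10 likewise gives the request for an emergency code break to the PI or the covering physician. It lists a SUSAR as a ground of its own, item 1(b). Only item 1(a) is tied to the allocation possibly affecting how the child is managed.

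Section 6.10 sets the blinding rule without a written exception: "All the following individuals will be blinded to the IMP allocation, the parent, the child, the research nurse, the local and chief PIs". Section 5.11.1 sets the consequence, also without an exception: "Children will be withdrawn from the study if their parents withdraw consent to participate, if their allocation is unblinded". On who judges the event, section 7.2.2 says: "Responsibility for evaluation of causality of adverse events will be shared between the treating the chief investigator and clinical co-principal investigators". Section 7.2.3 gives expectedness to the same roles.

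**The concern.** A step that serves only a regulatory report is sent through the people who are meant to stay blind. Suspected unexpected serious reactions are the events for which a blinded view of causality matters most. Nothing in sections 7.2 to 7.5 requires causality and expectedness to be recorded before the code is opened, so an investigator who knows the arm could still finalise or change them.

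The second consequence comes from section 5.11.1. Because the code was opened, the child is withdrawn, even if nobody treating the child needed the allocation. Further information on a child with suspected drug harm then depends on the parents agreeing to continued calls.

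**Working it through.** The point rests on no sample size, power or rate in the protocol, so the check is a side-by-side reading, followed by one bound on size.

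1. **Is unblinding compulsory?** Yes, under 7.5, for any suspected SUSAR in either arm. Section 5.10 is permissive, since a PI may request a break. The two sections therefore differ on whether it is required.
2. **What is the allocation for?** In 7.5, only to decide whether the sponsor reports to the MHRA. No clinical use is stated there.
3. **Who sets the break in motion?** The PI or covering physician (5.10), through site pharmacy staff (9.6.1). Neither section describes a route from code holder to sponsor that bypasses the PI.
4. **Does the PI learn the arm?** Probably. The PI makes the request, and no bypass is described. But no sentence says so, 7.5 names only the sponsor as recipient, and the SOP is not available.
5. **Is that consistent with 6.10?** Not for a reporting-only break. Local and chief PIs are on the list of blinded people.
6. **Was the PI route unavoidable?** No. In 5.10 item 2(a) a pharmacist is unblinded to reissue medication while other trial staff stay blind. The footnote in 5.6 places the key with the pharmacist and the Data Monitoring Committee. Section 7.4.2 already sends SUSARs to the sponsor's office (the JRO) within one working day. A separate code holder and a reporting line both exist, and 7.5 does not connect them.
7. **What follows for the child?** Withdrawal under 5.11.1. Section 6.7 does not name unblinding among its three circumstances for discontinuing trial medication, so the two sections do not match. This also touches the per-protocol analysis in 10.7, which drops data collected after discontinuation. Read literally, 5.11.1 would even catch the pharmacist's reissue unblinding in 5.10 item 2(a).
8. **Are outcome data lost?** In part at most. Section 5.11.3 asks parents whether calls may continue and keeps whatever is collected.

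**Size.** The protocol gives no expected number of SUSARs. Assume 1 to 5 among the 1300 children to be recruited:

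- lower end: 1/1300 = 0.08%
- upper end: 5/1300 = 0.38%

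At most about 4 children in 1000 would be affected, and their data would be only partly lost.

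**The case against.** The strongest defence has four parts.

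**Order of judgement.** Under 7.1.2 and 7.1.5 an event is a suspected SUSAR only once someone has judged it related, serious and unexpected. Causality must therefore be at least provisionally settled before 7.5 applies, and no section provides for reassessment afterwards. A reader might infer that causality will be decided with the arm known. The documents do not support that. What stands is narrower: nothing prevents the judgement from being finalised or revised after the break.

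**Disclosure.** A reader might take it as established that the PI is told the arm. It is an inference, though a strong one, because the unseen SOP could restrict who receives the result.

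**Deliberate exception.** Section 6.10 can be read as the general rule and 5.10 item 1(b) as a stated exception to it. That is fair for a break made for clinical need. It does not explain why a break whose only stated purpose is the sponsor's report should pass through the PI.

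**Effect on results.** A reader might infer a large distortion of the safety comparison. The protocol plans no comparison of arms by attributed causality. The safety endpoints in 10.1.2 are severe adverse events, withdrawal and mortality, 10.8 analyses adverse events descriptively, and the comparison that the Data Monitoring Committee may request (9.6.2) is of fatal or life-threatening events and other SAEs. The triggering event is already recorded under 7.4.2. Section 7.4.1 also classes the common reasons for admission as expected, which narrows what can become a SUSAR. This part of the defence stands in full. Nor does withdrawal amount to loss to follow-up: 5.11.3 offers the same calls, and any parent may stop at any time in any case (5.1.3).

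**Conclusion.** The inconsistency is in the text and is worth correcting, though its numerical effect is small. Section 7.5 compels unblinding for a purpose only the sponsor has, by a route that 5.10 and 9.6.1 place with the PI, whom 6.10 keeps blind. Section 5.11.1 then turns that reporting step into a withdrawal. Disclosure to the PI is probable, not certain, and depends on an SOP that is not shown.

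The effect on the primary rate ratio is negligible: under 0.4% of children even at 5 cases, which is an assumed figure. The rule applies to both arms before the allocation is known, so it does not favour either by design. What is at stake is the blinded assessment and continued follow-up of a few important cases.

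**What to change.** - **7.5, 5.10 item 1(b) and 9.6.1:** state that, when unblinding is for reporting only, the sponsor's office obtains the allocation directly from the code holder and does not disclose it to the PI, the chief investigator or the trial team. All three need the change, because amending 7.5 alone would leave item 1(b) contradicting it. The emergency route for clinical need stays as it is.
- **7.5:** require causality and expectedness to be recorded before the code is opened. This makes explicit the order that the definitions in 7.1 already imply.
- **5.11.1:** reconcile with 5.10 (including the reissue unblinding in item 2(a)), 6.7 and 7.5, so that the protocol says whether unblinding that is not disclosed to the trial team is meant to trigger withdrawal. Which rule applies is for the sponsor and investigators to decide.

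The cost is a wording amendment and a line in the code-break SOP. The small downside is that the sponsor's office needs a defined route to the code holder.
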